2.3 Treatment Assignment and Blinding

In Part 1, approximately 462 subjects will be randomized in a 2:1 ratio to DB upadacitinib 45 mg QD or matching placebo for 8 weeks. The randomization will be stratified by bio-IR status (bio-IR vs. non-bio-IR), corticosteroid use (yes vs. no) and Adapted Mayo score (≤ 7 vs. > 7) at Baseline. Within bio-IR, the randomization will be further stratified by number of prior biologic treatments (≤ 1 vs. > 1). Within non-bio-IR, the randomization will be further stratified by previous biologic use (yes vs. no).

All eligible subjects entering Part 2 will receive OL upadacitinib 45 mg QD for an additional 8 weeks (until Week 16).

The primary analysis will be performed after all ongoing subjects have completed the Induction Study activities and the database has been locked. Treatment assignments for the Induction Study will be unblinded to AbbVie for statistical analyses. The study sites and subjects will remain blinded to the DB induction treatment assignments until all subjects have completed the Maintenance Study.

2.4 Sample Size Determination

For the Induction Study (Part 1), approximately 462 subjects are expected to be randomized to upadacitinib 45 mg QD or placebo in a randomization ratio of 2:1. The sample size for this study is based on the expected proportion of subjects who achieve clinical remission per Adapted Mayo score at Week 8. Based on the results from Phase 2b upadacitinib Study M14-234 (Substudy 1), the proportions of subjects achieving clinical remission per Adapted Mayo score in upadacitinib 45 mg QD group and placebo

group are 19.6% and 0%, respectively. Considering the small sample size in Phase 2b study and more stringent definition of primary endpoint used for Phase 3 studies, clinical remission rate is assumed to be 5% in the placebo group and 18% in the upadacitinib 45 mg QD treatment group. Based on these assumptions, a sample size of 154 subjects in placebo and 308 subjects in upadacitinib dose will have > 95% power to detect the 13% treatment difference in the primary endpoint between upadacitinib 45 mg QD group and placebo group using two-sided Fisher's exact test at a 0.05 significant level.

3.0 Endpoints

The terminologies and efficacy variables are defined as below:

- **Mayo Score**
 - **Full Mayo Score:** composite score of UC disease activity based on the stool frequency subscore [SFS] (0 – 3), rectal bleeding subscore [RBS] (0 – 3), physician's global assessment [PGA] subscore (0 – 3) and endoscopic subscore (0 – 3). This score ranges from 0 – 12 points with higher scores representing more severe disease.
 - **Partial Mayo Score:** Full Mayo score minus the endoscopic subscore.
 - **Adapted Mayo Score:** Full Mayo score minus the PGA subscore.
 - **Partial Adapted Mayo Score:** Adapted Mayo score minus the endoscopic subscore.
- **Clinical Remission**
 - **per Full Mayo Score:** Full Mayo score ≤ 2 with no subscore > 1 .
 - **per Adapted Mayo Score:** Adapted Mayo score ≤ 2 , with SFS ≤ 1 and not greater than baseline, RBS of 0, and endoscopic subscore ≤ 1 .
 - **per Partial Mayo Score:** Partial Mayo score ≤ 2 , with no subscore > 1 .
- **Clinical Response**
 - **per Full Mayo Score:** decrease in Full Mayo score of ≥ 3 points and $\geq 30\%$ from Baseline, PLUS a decrease in RBS ≥ 1 or an absolute RBS ≤ 1 .

- **per Adapted Mayo Score:** decrease in Adapted Mayo score ≥ 2 points and $\geq 30\%$ from Baseline, PLUS a decrease in RBS ≥ 1 or an absolute RBS ≤ 1 .
- **per Partial Mayo Score:** decrease in Partial Mayo score ≥ 2 points and $\geq 30\%$ from Baseline, PLUS a decrease in RBS ≥ 1 or an absolute RBS ≤ 1 .
- **per Partial Adapted Mayo Score:** decrease in Partial Adapted Mayo score ≥ 1 point and $\geq 30\%$ from Baseline, PLUS a decrease in RBS ≥ 1 or an absolute RBS ≤ 1 .
- **Endoscopic Improvement:** Endoscopic subscore of 0 or 1.
- **Endoscopic Remission:** Endoscopic subscore of 0.
- **Histologic Improvement:** decrease from Baseline in Geboes score.
- **Histologic Endoscopic Mucosal Improvement:** Endoscopic subscore of 0 or 1 and Geboes score ≤ 3.1 .
- **Mucosal Healing:** Endoscopic score of 0 and Geboes score < 2.0 .

Note: Evidence of friability during endoscopy in subjects with otherwise "mild" endoscopic activity will confer an endoscopic subscore of 2.

3.1 Primary Endpoint

The primary efficacy endpoint is the achievement of clinical remission per Adapted Mayo score at Week 8 in Part 1.

3.2 Secondary Endpoints

The ranked secondary efficacy endpoints for Part 1 under overall type I error control are as follows:

1. The achievement of endoscopic improvement at Week 8;
2. The achievement of endoscopic remission at Week 8;
3. The achievement of clinical response per Adapted Mayo score at Week 8;

4. The achievement of clinical response per Partial Adapted Mayo score at Week 2;
5. The achievement of histologic-endoscopic mucosal improvement at Week 8;
6. The achievement of no bowel urgency at Week 8;
7. The achievement of no abdominal pain at Week 8;
8. The achievement of histologic improvement at Week 8;
9. Change from Baseline in IBDQ total score at Week 8;
10. The achievement of mucosal healing at Week 8;
11. Change from Baseline in FACIT-F score at Week 8.

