5.2.1 Inclusion Criteria

A subject will be eligible for study participation if he/she meets the following criteria:

1. Male or female ≥ 16 and ≤ 75 years of age at Baseline.
 - Adolescent subjects at the age of 16 and 17 years old will be enrolled if approved by the country or regulatory/health authority. If these approvals have not been granted, only subjects ≥ 18 years old will be enrolled.
 - Adolescent subjects at the age of 16 and 17 years old must weigh ≥ 40 kg and meet the definition of Tanner Stage 5 (refer to [Appendix J](#)) at the screening Visit.
2. Diagnosis of UC for 90 days or greater prior to Baseline, confirmed by colonoscopy during the Screening Period, with exclusion of current infection, colonic dysplasia and/or malignancy. Appropriate documentation of biopsy results consistent with the diagnosis of UC, in the assessment of the Investigator, must be available.
3. Active UC with an Adapted Mayo Score of 5 to 9 points and endoscopy subscore of 2 to 3 (confirmed by central reader).
4. Demonstrated an inadequate response to, loss of response to, or intolerance to at least one of the following treatments including, oral aminosalicylates, corticosteroids, immunosuppressants and/or biologic therapies, in the opinion of the investigator as defined below:

Note: An inadequate response, loss of response, or intolerance to Oral Aminosalicylates will NOT count towards eligibility for the following countries: Austria, Czechia, Finland, France, Ireland, Italy, Latvia, Lithuania, Norway, Poland, Portugal, Spain, Sweden and United Kingdom.

- Oral aminosalicylates (e.g., mesalamine, sulfasalazine, olsalazine, balsalazide)
 - Signs and symptoms of persistently active disease, in the opinion of the investigator, during a current or prior course of at least 4 weeks of

treatment with 2.4 g/day mesalamine, 4 g/day sulfasalazine, 1 g/day olsalazine, or 6.75 g/day balsalazide.

- Corticosteroids
 - Signs and symptoms of persistently active disease despite a history of at least one induction regimen that included a dose equivalent to prednisone ≥ 40 mg/day orally for at least 3 weeks or intravenously for 1 week, OR
 - Unable to taper corticosteroids to below a dose equivalent to prednisone 10 mg daily orally without recurrent active disease, OR
 - Signs and symptoms of persistently active disease during or after a course of at least 4 weeks of treatment with 9 mg/day budesonide or 5 mg/day beclomethasone, OR

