8.1.3 Definition of Missing Data Imputation

Missing data will be imputed using one or more of the following methods:

Non-Responder Imputation (NRI): In NRI analyses, subjects who prematurely discontinue the study prior to efficacy assessment at Week 8 of Substudy 1 or Substudy 2 Part 1, Week 16 of Substudy 2 Part 2, and Week 44 or Week 52 of Substudy 3 will be considered non-responders with respect to the efficacy endpoint.

Observed Cases (OC): The OC analysis will not impute values for missing evaluations, and thus a subject who does not have an evaluation on a scheduled visit will be excluded from the OC analysis for that visit.

Depending on the magnitude of missing data due to COVID-19, additional appropriate analysis of missing data may be performed with details included in the SAP. The primary approach for handling missing data in the analysis of binary endpoints will use Non-Responder Imputation while incorporating Multiple Imputation (MI) to handle missing data due to COVID-19 (NRI-C). At each visit, subjects will be characterized as responders or non-responders based on MI imputed values if missing due to COVID-19; otherwise, subjects will be considered as non-responders for missing due to other reasons in the NRI-C approach.

For continuous endpoints, missing data will be handled using Mixed-Effect Model Repeat Measurement (MMRM).

The SFS and RBS at an assessment visit will be calculated as an average of the entries recorded into the subject's diary from the most recent consecutive 3-day period prior to each study visit. If diary entries from the 3 consecutive days prior to the visit are not available, the 3 most recent consecutive days in the last 10 days will be utilized. If data are not available for 3 consecutive days, the average of the entries from the most recent 3 non-consecutive days in the last 10 days will be utilized. If less than 3 days of diary data are available, SFS and RBS will be considered missing. Clinical endpoints of abdominal pain and bowel urgency from subject diaries will be measured at the same time period as the SFS and RBS.

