3.2 Secondary Endpoints

The ranked secondary efficacy endpoints under overall type I error control are as follows:

1. The achievement of endoscopic improvement at Week 52;
2. The achievement of clinical remission per Adapted Mayo score at Week 52 among subjects who achieved clinical remission at the end of the induction treatment in the Induction Study;
3. The achievement of clinical remission per Adapted Mayo score at Week 52 and corticosteroid free for ≥ 90 days immediately preceding Week 52 among subjects

who achieved clinical remission at the end of the induction treatment in the Induction Study;

4. The achievement of endoscopic improvement at Week 52 among subjects who achieved endoscopic improvement at the end of the induction treatment in the Induction Study;
5. The achievement of endoscopic remission at Week 52;
6. The achievement of clinical response per Adapted Mayo score at Week 52 among subjects who achieved clinical response at the end of the induction treatment in the Induction Study;
7. The achievement of histologic-endoscopic mucosal improvement at Week 52;
8. Change from Baseline in IBDQ total score at Week 52;
9. The achievement of mucosal healing at Week 52;
10. The achievement of no bowel urgency at Week 52;
11. The achievement of no abdominal pain at Week 52;
12. Change from Baseline in FACIT-F score at Week 52;

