1. For each of the ranked binary secondary endpoints (Section 3.2), greater proportion of subjects with improvement for the endpoint is achieved with upadacitinib 45 mg QD when compared to placebo;
2. For each of the ranked continuous endpoints (Section 3.2), greater mean change from baseline for the endpoint is achieved with upadacitinib 45 mg QD when compared to placebo.

The estimands corresponding to the secondary efficacy objectives are defined for each of the binary ranked secondary endpoints as follows: difference in the percentage of subjects achieving binary endpoints regardless of premature discontinuation of study drug and without initiation or dose escalation of UC-related corticosteroids (See Section 8.2.2) in the upadacitinib 45 mg QD and placebo groups in the ITT population.

The estimands corresponding to the secondary efficacy objectives are defined for each of the continuous ranked secondary endpoints as follows: difference in the mean change from baseline regardless of premature discontinuation of study drug and if subjects would not initiate or escalate dose of UC-related corticosteroids (See Section 8.2.2) in the upadacitinib 45 mg QD and placebo groups in the ITT population.

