8.0 Efficacy Analyses

8.1 General Considerations

The efficacy analyses for the 8-week DB induction period (Part 1) will be conducted in the ITT1 population. The efficacy analyses for the 8-week OL extended treatment period (Part 2) will be conducted in the ITT2 population. All tests will be at the α level of 0.05

(2-sided). "Baseline" refers to the last non-missing observation prior to the first administration of the study drug or prior to the randomization if no study drug is given.

The primary analysis will be performed after all ongoing subjects have completed the study activities up to Week 16 and the database has been locked. This will be the only and final analysis for the primary and secondary efficacy endpoints as well as all other efficacy endpoints in the Induction Study.

Unless otherwise specified, categorical variables will be analyzed using Cochran-Mantel-Haenszel (CMH) test, stratified by bio-IR status (bio-IR vs. non-bio-IR), Baseline corticosteroid use (yes vs. no) and Baseline Adapted Mayo score (≤ 7 vs. > 7). Any subject who was randomized under the wrong stratum will be analyzed according to the actual stratum the subject belongs to. Continuous variables collected longitudinally will be analyzed using Mixed-Effect Model Repeat Measurement (MMRM) method. Continuous variables collected at only one post-baseline visit (such as Mayo score) will be analyzed using an Analysis of Covariance (ANCOVA) model.

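### The ranked no-bowel-urgency and no-abdominal-pain endpoints can already be met at entry, and their CMH analysis does not adjust for the subject's own symptom status at Baseline (Substudy 2) or Week 0 (Substudy 3)

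*SAP*

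**What the plan says.** Substudy 2 SAP section 3.2 ranks "The achievement of no bowel urgency at Week 8" sixth and "The achievement of no abdominal pain at Week 8" seventh. Substudy 3 SAP section 3.2 ranks "The achievement of no bowel urgency at Week 52" tenth, with abdominal pain eleventh. No symptom at entry and no change from entry is required. Protocol section 8.1.3 gives the source: "Clinical endpoints of abdominal pain and bowel urgency from subject diaries will be measured at the same time period as the SFS and RBS".

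The disease-activity entry criterion in Protocol section 5.2.1 is "Active UC with an Adapted Mayo Score of 5 to 9 points and endoscopy subscore of 2 to 3". That score is built from stool frequency, rectal bleeding and endoscopy.

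In Substudy 2 the CMH test is "stratified by bio-IR status (bio-IR vs. non-bio-IR), Baseline corticosteroid use (yes vs. no) and Baseline Adapted Mayo score" (SAP section 8.1, cut at 7). In Substudy 3 the strata are bio-IR status, Week 0 clinical remission and Week 0 corticosteroid use. Urgency and pain status appear in neither set, and neither baseline table (section 7.1 of each SAP) lists the two diary symptoms.

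The data exist. The diary is dispensed at Screening (Protocol section 5.3.1.1) and records both symptoms (section 10.3). Both SAPs put the Baseline measurement into the multiple imputation model (section 8.3.1), and Table D-1 of each includes urgency and pain among the imputed items.

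**The concern.** A subject with no urgency at Baseline who still has none at Week 8 counts as an achiever, provided the visit is assessed (or missing because of COVID-19 and imputed as symptom-free) and no corticosteroid intercurrent event has occurred. Such subjects raise the rate in both arms without having improved. A reader of the Substudy 2 tables could not tell how many achievers began without the symptom.

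The subject's own starting status is also likely to be a strong predictor of later status. Leaving it out gives up precision on endpoints under type I error control. In Substudy 2 the sequence is fixed, so ranks 6 and 7 gate ranks 8 to 11, including IBDQ, mucosal healing and FACIT-F.

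**Working it through.** **1. The plan's own figures.** Sample size rests on the primary endpoint only. Exact Fisher power is 98.9% for Substudy 2 (154 vs 308, 5% vs 18%, two-sided 0.05) and 99.97% for Substudy 3 (150 vs 150, 12% vs 40%, two-sided 0.025). Both agree with the stated power above 95%, and this point does not affect them. The documents give no rate or power for urgency or pain.

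**2. What can be met at entry in Substudy 2.** Entry endoscopy is 2 or 3, so endoscopic improvement, endoscopic remission, histologic-endoscopic improvement and mucosal healing are out of reach at Baseline. The two clinical response endpoints and histologic improvement require a decrease. IBDQ and FACIT-F are changes. Only urgency and pain can already be satisfied.

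**3. How many might enter symptom-free (assumption).** Let the daily urgency probability vary between subjects as Beta(a, b). The chance of three urgency-free days is b(b+1)(b+2) / [(a+b)(a+b+1)(a+b+2)]. With an assumed a+b = 2:
- mean 0.70 (b = 0.6): 2.496/24 = 10.4%
- mean 0.80 (b = 0.4): 1.344/24 = 5.6%
- mean 0.90 (b = 0.2): 0.528/24 = 2.2%

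Other spreads change these figures, and there is no such model for pain. The calculations below use 5% and 10%.

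**4. Substudy 2 variance.** Let q be the share symptom-free at Baseline, p the achievement rate among symptomatic subjects and r the rate among symptom-free subjects. Per arm, P = (1−q)p + qr.
- Ignoring entry status: V1 = sum over arms of P(1−P)/n.
- Stratifying on it (large strata): V2 = sum over arms of [(1−q)p(1−p) + qr(1−r)]/n.

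Worked case: q = 10%, p = 15% vs 45%, r = 70% vs 80% (placebo vs upadacitinib).
- Placebo 0.9×0.15 + 0.1×0.70 = 0.205; upadacitinib 0.9×0.45 + 0.1×0.80 = 0.485; difference 0.28.
- V1 = 0.205×0.795/154 + 0.485×0.515/308 = 0.0018692.
- V2 = 0.9×(0.1275/154 + 0.2475/308) + 0.1×(0.21/154 + 0.16/308) = 0.0016567.
- Reduction 1 − 0.0016567/0.0018692 = 11.4%. Symptom-free entrants are 0.07/0.205 = 34% of placebo achievers.

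| Assumed p; r (placebo/upadacitinib) | q | Difference (points) | Symptom-free entrants among placebo achievers | Variance reduction |
|---|---|---|---|---|
| 15/45; 70/80 | 5% | 29.0 | 20% | 6.4% |
| 15/45; 70/80 | 10% | 28.0 | 34% | 11.4% |
| 20/32; 60/70 | 5% | 11.9 | 14% | 3.9% |
| 20/32; 60/70 | 10% | 11.8 | 25% | 7.0% |

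Other assumed rates at the same two shares gave 3% to 14%. In the 20/32 case, normal-approximation power at two-sided 0.05 rises from 79.2% to 80.7% (q = 5%) and from 76.6% to 79.5% (q = 10%).

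**5. Allowing for the planned strata.** V1 is unstratified, whereas the plan is an eight-stratum CMH. Simulating eight against sixteen strata, with assumed stratum shares and no prognostic value given to the existing factors, lowers the first scenario's reductions to about 4–5% (q = 5%) and 9–10% (q = 10%). In the 20/32 scenario, power moves from 76.7% to 77.8% and from 74.2% to 76.5%. In the 15/45 scenario, power is essentially 100% either way.

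**6. Substudy 3.** With 150 per arm, 30% to 70% symptom-free at Week 0 and four assumed sets of rates, the variance falls by 3% to 18% before allowing for what the Week 0 remission stratum already explains.

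**The case against.** The strongest reply is that nothing is in error. Analysing by the main randomisation factors is a standard prespecified choice, and a further prognostic factor is optional. A reader might infer bias or an inflated type I error; randomisation excludes both.

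The size is wholly assumed, and this stands. The protocol's introduction names rectal urgency among the hallmark symptoms, which points to few urgency-free entrants. A reader might take a 20% symptom-free case, where over half of placebo achievers (0.14/0.26 = 54% at the 15/45 rates) never had the symptom. That share is about twice the largest given by the model in step 3, and nothing in the documents supports it.

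A reader might also say that Week 0 status is ignored in Substudy 3. It is not: clinical remission at Week 0 is a stratum and a partial proxy, and only the specific symptom is missing. In a maintenance trial of responders, staying symptom-free from Week 0 to Week 52 is an intended success, and absence at Week 0 does not mean absence at induction Baseline. The interpretability complaint therefore belongs to Substudy 2.

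The hypothesis wording, "greater proportion of subjects with improvement for the endpoint is achieved with upadacitinib 45 mg QD when compared to placebo", is weak evidence of a contradiction. It covers all ranked binary endpoints, and the estimand in the same section speaks of achieving them.

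Some change-based symptom evidence is planned (IBDQ bowel items, UC-SQ), and their scores are in the baseline tables. They do not give entry status on the diary items that define these endpoints.

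Finally, a CMH factor does not stop symptom-free entrants counting as achievers. That is correct, and it is why the supportive table is needed as well.

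**Conclusion.** The point holds as a matter of precision in both substudies and of interpretability in Substudy 2. Entry symptom status is collected and already feeds the imputation model. The continuous analyses adjust for the Baseline value, but these two binary comparisons do not. Under the assumed rates, with 5% to 10% symptom-free at Baseline, the Substudy 2 variance would fall by roughly 4% to 11%, somewhat less once existing strata and sparse cells are counted. The Substudy 3 gain depends on how much Week 0 remission already captures. If the true effect is large, no test result is likely to change. A reader might extend the point to unranked threshold endpoints such as fecal calprotectin or IBDQ remission; those lie outside the type I error control, and the extension is not made here.

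**What to change.** For the urgency and pain endpoints only, add the subject's own symptom status (present or absent, same diary window and derivation rule as the endpoint) as a CMH stratification factor: Baseline in Substudy 2, Week 0 in Substudy 3. Keep the ITT population and the ranking.

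In Substudy 2, also tabulate the rates and difference among subjects with the symptom at Baseline as a supportive analysis, and add urgency and pain to the baseline table. Do not restrict the main analysis to symptomatic subjects, because that does not reliably gain power. In the 20/32 scenario with 30% symptom-free, restricted power is 67.1% against 67.9% unrestricted.

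The cost is SAP wording and programming on data already collected. Strata rise from 8 to 16 and some will be sparse. At 5% symptom-free, about 8 placebo subjects (154×0.05 = 7.7) would be spread over eight new cells, and a cell containing only one arm contributes nothing. The protocol states that all Substudy 2 subjects have completed induction. If either substudy is already unblinded, the added analysis there should be labelled supportive.

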3.3 Other Efficacy Endpoints

The following additional efficacy endpoints will be evaluated for Part 1:

- The achievement of response in IBDQ Bowel Symptom domain (defined as increase of IBDQ bowel symptom domain score ≥ 6 from Baseline) at Week 8;
- The achievement of response in IBDQ fatigue item (defined as increase of IBDQ fatigue item score ≥ 1 from Baseline) at Week 8;
- The achievement of SFS of 0, RBS of 0 and endoscopic subscore of 0 at Week 8;
- The achievement of SFS of 0, RBS of 0 and endoscopic subscore of ≤ 1 at Week 8;
- The achievement of clinical remission per Full Mayo score at Week 8;
- Change in Full Mayo score from Baseline at Week 8;
- The achievement of clinical remission per Partial Mayo score over time;
- The achievement of clinical response per Partial Adapted Mayo score over time;
- The achievement of clinical response per Partial Mayo score over time;
- The achievement of SFS ≤ 1 over time;
- The achievement of RBS of 0 over time;

- The achievement of Fecal calprotectin below 150 mg/kg over time;
- Change from Baseline in fecal calprotectin over time;
- Change from Baseline in hs-CRP over time;
- Change from Baseline in Partial Adapted Mayo score, Partial Mayo score and SFS, RBS over time;
- Change from Baseline in UCEIS score over time;
- Change from Baseline in laboratory and nutritional parameters (e.g., hemoglobin, hematocrit, albumin, total protein concentration, and weight);
- Change from Baseline in subject-reported stool frequency (absolute values) over time;
- Change from Baseline in IBDQ total and domain score over time;
- Change from Baseline in individual IBDQ item under Bowel Symptom domain (for Q1, Q5, Q9, Q13, Q17, Q20, Q22, Q24, Q26, and Q29) over time;
- The achievement of IBDQ response (defined as increase of IBDQ total score ≥ 16 from Baseline) over time;
- The achievement of IBDQ remission (defined as IBDQ total score ≥ 170) over time;
- Change from Baseline in EQ-5D-5L score over time;
- Change from Baseline in WPAI scores over time;
- Change from Baseline in SF-36 Physical Component Summary (PCS) and Mental Component Summary (MCS) components and domain scores over time;
- Summary of PGIC improvement category over time;
- Summary of PGIS severity category over time;
- Change from Baseline in FACIT-F score over time;
- Change from Baseline in UC-SQ score over time;
- UC-related hospitalizations through Week 8;
- UC-related surgeries through Week 8;
- All-cause hospitalizations through Week 8;
- All-cause surgeries through Week 8.

The following additional efficacy endpoints will be evaluated for Part 2:

- The achievement of clinical remission per Adapted Mayo score at Week 16;
- The achievement of endoscopic improvement at Week 16;
- The achievement of endoscopic remission at Week 16;
- The achievement of clinical response per Adapted Mayo score at Week 16;
- The achievement of clinical response per Partial Adapted Mayo score at Week 10;
- The achievement of histologic-endoscopic mucosal improvement at Week 16;
- The achievement of no bowel urgency at Week 16;
- The achievement of no abdominal pain at Week 16;
- The achievement of histologic improvement at Week 16;
- Change from Baseline in IBDQ total score at Week 16;
- The achievement of mucosal healing at Week 16;
- Change from Baseline in FACIT-F score at Week 16.

